3. INTRODUCTION

Progressive supranuclear palsy (PSP) is a rare neurodegenerative disorder that leads to death in an average of 7 years following symptom onset [Williams 2005]. The National Institute of Neurological Disorders and Stroke (NINDS), the National Organization for Rare Disorders (NORD), and the European Organisation for Orphan Diseases estimate the prevalence of PSP to be between 3 and 6 per 100,000 persons. Both the NINDS and NORD estimate that there are approximately 20,000 cases of PSP in the United States and 30,000 in the European Union, while there are thought to be approximately 17,000 cases in Japan [Takigawa 2016].

The disease is characterized by progressive aberrations in gait, eye movements, dysphagia, dysarthria, pseudobulbar affect, neuropsychiatric abnormalities, and dementia, as well as difficulties with sleep [Boxer 2017; Nath 2003]. Since the syndrome was first characterized in 1963, it is now recognized that there are a number of different clinical presentations that appear to be linked to the regional distribution and severity of pathology in the brain [Williams 2007]. There is currently no treatment available to stop or slow the progression of this deadly disease.

The neuropathological hallmark of PSP is the presence of neurofibrillary tangles in clinically correlated regions of the brain, including the basal ganglia, diencephalon, brainstem, and cerebellum with restricted involvement of the neocortex [Dickson 2010]. The tangles are composed of tau, an intracellular microtubule-associated protein, of which fragments may also be released into the cerebrospinal fluid (CSF) and interstitial space as N-terminal tau [Bright 2015; Guo 2017]. Tau dysfunction is thought to play a key role in the pathophysiology of PSP, both by causing neuronal dysfunction via tau aggregation into neurofibrillary tangles and by facilitating cell to cell spreading of tau pathology via secreted N-terminal tau.

BIIB092 is a humanized monoclonal antibody (mAb) that binds to amino acid residues 15 to 22 of N-terminal tau, removing it from the CSF. It is hypothesized that BIIB092-mediated depletion of N-terminal tau will inhibit the spread of tau pathology, potentially slowing the progression of PSP. This would be expected to translate into important improvements in function, activities of daily living, health outcomes, and overall quality of life for patients living with PSP.

3.1. Study Rationale

The neuropathological hallmark of PSP is the presence of tau pathology in the form of neurofibrillary tangles in characteristic subcortical and cortical brain regions. N-terminal tau is implicated in mediating the transcellular spreading of this tau pathology in PSP.

BIIB092 has been shown to bind N-terminal tau and suppress CSF concentrations of unbound N-terminal tau (i.e., N-terminal tau that is not bound to BIIB092) in preclinical studies, a single ascending dose (SAD) study in normal healthy volunteers (NHVs) (Study CN002001), and a multiple ascending dose (MAD) study in participants with PSP (Study CN002003). Based on these data, BIIB092 is expected to prevent spreading of tau pathology by binding and reducing unbound N-terminal tau in brain interstitial fluid, suggesting that it has potential utility for the treatment of human tauopathies, such as PSP.

The aim of this study is to demonstrate the efficacy of BIIB092 in delaying the progression of clinical signs and symptoms of PSP and to characterize its safety/tolerability profile.

CONFIDENTIAL

The information contained herein may not be used, disclosed, or published without the written consent of Biogen MA Inc.

3.2. Background

BIIB092 (formerly known as BMS-986168 and IPN007) is a humanized mAb of subclass IgG4 that specifically binds the microtubule-associated protein tau. BIIB092 is derived from the murine IgG1 mAb, IPN002, which was produced in response to immunization of mice with aggregated, recombinant full-length human tau (tau isoform 2N4R). The affinity, specificity, and functional activity of the antibody were maintained following humanization. BIIB092 recognizes a linear, amino terminal epitope (including amino acid residues 15 to 22 of full-length human tau) of tau. BIIB092 exhibits high affinity for human and cynomolgus monkey tau, with binding affinities of 7×10^{-10} M and 6.35×10^{-10} M, respectively. The primary site of action of BIIB092 is believed to be the interstitial space between neurons where it binds N-terminal tau, thereby reducing tau-induced neuronal hyperexcitability and tau-mediated spread of tau pathology.

BIIB092 is being developed for the treatment of PSP, a rare neurodegenerative disease associated with tau pathology that results in a progressive movement disorder. There is a significant unmet medical need for safe and effective agents for patients with PSP, as there are currently no approved drugs for its treatment. Existing medical management is focused on reducing symptoms, using drugs approved for various other indications off-label along with dietary supplements. However, it is widely accepted that none of these drugs is particularly effective in treating PSP.

BIIB092 was first introduced into clinical trials in the Phase 1 trials conducted in the United States (US), Study CN002001 in healthy adult volunteers and Study CN002003 in participants with PSP.

Results from the first-in-human study, CN002001, indicate that administration of single doses of up to 4200 mg of BIIB092 in healthy volunteers is well tolerated. Mean suppression of the CSF-unbound N-terminal tau in that study ranged from 67% to 97% at doses ranging from 70 to 4200 mg.

Study CN002003 was a Phase 1b randomized, double-blind, placebo-controlled, MAD study to characterize the safety, tolerability, pharmacokinetics (PK), pharmacodynamics (PD), and immunogenicity of BIIB092 doses of 150, 700, and 2100 mg in participants with PSP. All 3 doses were well tolerated based on results from the dose escalation phase of the study. Treatment with monthly doses of BIIB092 decreased CSF-unbound N-terminal tau by mean values of approximately 90%, 93%, and 96% on Day 29 and 91%, 95%, and 97% on Day 85 at doses of 150, 700, and 2100 mg, respectively.

Study 251PP201 is an ongoing open-label extension study to evaluate the long-term safety and tolerability of multiple doses of BIIB092 in participants with PSP who participated in CN002003.

A more detailed description of the chemistry, pharmacology, and safety of BIIB092 is provided in the Investigator's Brochure.

3.2.1. Research Hypothesis

This study will demonstrate that BIIB092 is effective and safe for the treatment of participants with PSP.

CONFIDENTIAL

The information contained herein may not be used, disclosed, or published without the written consent of Biogen MA Inc.

3.3. Benefit/Risk Assessment

The benefit/risk profile of BIIB092 in nonclinical studies, the SAD study in NHVs (Study CN002001), and the MAD study and its associated open-label extension study (Studies CN002003 and 251PP201, respectively) supports further evaluation of the safety, tolerability, immunogenicity, PK, PD response, and clinical efficacy of BIIB092 in participants with PSP.

BIIB092 is a humanized IgG4 isotype antibody that is considered to have a low potential for immunogenicity in humans based on nonclinical studies. There were no adverse effects noted at any dose tested in the pivotal toxicity studies in monkeys. Nonclinical findings were limited to decreases in CSF unbound N-terminal tau consistent with the intended pharmacology of BIIB092. In completed clinical study CN002001, there was no consistent trend showing a potential effect of anti-drug antibody (ADA) on the PK of BIIB092. In completed clinical study CN002003, there was no apparent dose-related trend in the number of subjects with positive immunogenicity results post-treatment.

Studies evaluating the potential for reproductive and developmental toxicity have not been performed for BIIB092.

As of 25 November 2018, an estimated 486 participants have been exposed to BIIB092 across all completed (Studies CN002001 and CN002003) and ongoing clinical studies (Studies 251PP201, 251PP301, and 251AD201). Based on safety data from a completed Phase 1 study in healthy volunteers (Study CN002001) and a completed Phase 1B study in participants with PSP (Study CN002003), the benefit/risk profile of BIIB092 was favorable to support further clinical development.

There is no information available about possible interaction of BIIB092 with other drugs, although no PK interactions are anticipated.

More detailed information about the known and expected benefits and risks and reasonably anticipated AEs of BIIB092 may be found in the Investigator's Brochure. However, because BIIB092 is an experimental agent, it is possible that unforeseen, unknown, or unanticipated reactions may occur.

CONFIDENTIAL

The information contained herein may not be used, disclosed, or published without the written consent of Biogen MA Inc.

4. STUDY OBJECTIVES AND ENDPOINTS

Objective	Endpoint
Primary	
To evaluate the efficacy of BIIB092, compared to placebo, as measured by a change from baseline in the PSP Rating Scale (PSPRS) at Week 52.	The primary efficacy endpoint will be evaluated by comparing the change from baseline in the total PSPRS score at Week 52 in participants treated with BIIB092 relative to the change in the total PSPRS score in participants treated with placebo.
To assess the safety and tolerability of BIIB092, relative to placebo, by measuring the frequency of deaths, SAEs, and AEs leading to discontinuation, and Grade 3 & 4 laboratory abnormalities.	The primary safety endpoint will be evaluated by tabulating the numbers and percentages of deaths and unique participants with SAEs and AEs leading to discontinuation, and Grade 3 & 4 laboratory abnormalities.
Key Secondary	
To evaluate the efficacy of BIIB092, compared to placebo, as measured by a change from baseline in the Movement Disorder Society-sponsored revision of the Unified Parkinson's Disease Rating Scale (MDS-UPDRS) Part II at Week 52.	The impact of BIIB092 on the MDS-UPDRS Part II will be evaluated relative to the change from baseline at Week 52 in the BIIB092-treated participants and compared to that of the placebo-treated participants.
To evaluate the efficacy of BIIB092, compared to placebo, as measured by the Clinical Global Impression of Change (CGI-C) at Week 52.	The impact of BIIB092 on the CGI-C scale score will be evaluated at Week 52 in the BIIB092-treated participants and compared to that of the placebo-treated participants.
To evaluate the efficacy of BIIB092, compared to placebo, as measured by a change from baseline in the Repeatable Battery for the Assessment of Neuropsychological Disease Severity (RBANS) at Week 52.	The impact of BIIB092 on the RBANS scale will be evaluated relative to the change from baseline at Week 52 in the BIIB092-treated participants and compared to that of the placebo-treated participants.
To assess the impact of BIIB092 on quality of life, relative to placebo, as measured by change from baseline on the Progressive	The impact of BIIB092 on the PSP-QoL will be evaluated relative to the change from baseline at Week 52 in the BIIB092-treated

CONFIDENTIAL

The information contained herein may not be used, disclosed, or published without the written consent of Biogen MA Inc.


Supranuclear Palsy Quality of Life scale (PSP-QoL) at Week 52.
	
participants and compared to that of the placebo-treated participants.

Other Secondary
	

To assess the efficacy of BIIB092, relative to placebo, as measured by a change from baseline at Week 48 (Week 52 for Clinical Global Impression of Severity [CGI-S]) on the following instruments:
 
 • Schwab and England Activities of Daily Living (SEADL) Scale • CGI-S • Phonemic Fluency Test • Letter-Number Sequencing (LNS) Test • Color Trails Test (CTT) • Montreal Cognitive Assessment (MoCA) 	
The impact of BIIB092 on the following instruments:
 
 • SEADL Scale • CGI-S • Phonemic Fluency Test • LNS Test • CTT • MoCA 
will be evaluated relative to the change from baseline at Week 48 (Week 52 for CGI-S) in the BIIB092-treated participants and compared to that of the placebo-treated participants.

To assess the immunogenicity of BIIB092.
	
Immunogenicity of BIIB092 will be measured by assessment of the presence or absence of anti-BIIB092 antibodies in serum.

To assess the efficacy of BIIB092, relative to placebo, as measured by absolute and percent change from baseline of brain volumes, as determined by magnetic resonance imaging (MRI), at Week 52 in the following regions:
 
 • Ventricles • Whole brain • Midbrain • Pons • Superior cerebellar peduncle • Third ventricle • Frontal lobe 	
The impact of BIIB092 on brain volumes, as determined by MRI in the following regions:
 
 • Ventricles • Whole brain • Midbrain • Pons • Superior cerebellar peduncle • Third ventricle • Frontal lobe 
will be evaluated relative to the absolute and percent changes from baseline at Week 52 in the BIIB092-treated participants and compared to that of the placebo-treated participants.

CONFIDENTIAL

The information contained herein may not be used, disclosed, or published without the written consent of Biogen MA Inc.

Tertiary/Exploratory	

[REDACTED]
 
[REDACTED]
 
[REDACTED]
 
• [REDACTED]• [REDACTED]• [REDACTED]	
[REDACTED]
 
• [REDACTED]• [REDACTED]• [REDACTED] 
[REDACTED]
 
[REDACTED]
 
[REDACTED]


[REDACTED]
 
[REDACTED]
 
[REDACTED]
 
• [REDACTED]• [REDACTED]	
[REDACTED]
 
• [REDACTED]• [REDACTED] 
[REDACTED]
 
[REDACTED]
 
[REDACTED]

[REDACTED]
 
[REDACTED]
 
[REDACTED]
	
[REDACTED]
 
[REDACTED]
 
[REDACTED]
 
[REDACTED]
 
[REDACTED]
 
[REDACTED]
 
[REDACTED]
 
[REDACTED]
 
[REDACTED]

[REDACTED]
 
[REDACTED]
	
[REDACTED]
 
[REDACTED]
 
[REDACTED]

[REDACTED]
	
[REDACTED]
 
 • [REDACTED] • [REDACTED] [REDACTED] [REDACTED] [REDACTED] [REDACTED] [REDACTED] [REDACTED] • [REDACTED] • [REDACTED] [REDACTED] [REDACTED] [REDACTED]

Open-Label Extension Period
	

To assess the long-term safety and tolerability of BIIB092 in participants with PSP.
	
The tertiary endpoint will be incidence of AEs, SAEs, and SAEs accompanied by death.

To assess the long-term efficacy of BIIB092 in participants with PSP.
	
The tertiary endpoints will be change from baseline over the placebo-controlled period and long-term extension period for clinical and health-outcomes assessments.
 
This study includes an optional substudy to measure quantitative movement assessments (QMAs) using wearable sensors. The QMAs will measure gait, postural instability, motor function, and falls in a subset of participants participating in the long-term extension period.

CONFIDENTIAL

[figure not shown]
The information contained herein may not be used, disclosed, or published without the written consent of Biogen MA Inc.

5. STUDY DESIGN

5.1. Overall Design

The study design schematic is presented in [Figure 1](#).

Figure 1: Study Design Schematic

This is a randomized, double-blind, placebo-controlled, parallel-group study to evaluate the efficacy and safety of intravenously administered BIIB092 in participants with PSP with an open-label extension period.

5.1.1. Overall Study Design

The study design schematic is presented in [Figure 1](#). The study will consist of a 52-week double-blind treatment period, which will be followed by a long-term open-label extension period for follow up. Participants will be randomized to receive BIIB092 or placebo. Approximately 459 participants in total will be randomized in a 2:1 ratio to receive BIIB092 or placebo (306 participants active or 153 placebo). In the double-blind treatment period of the study, participants will be dosed approximately once every 4 weeks (Q4W) up to a total of 13 times, with the last dose of study treatment of the double-blind period (Dose 13) administered at Week 48.

At Week 52, participants completing the double-blind treatment period may choose to continue into the open-label extension period of the study. Participants who wish to continue in the open-label extension period will receive the first dose of the open-label study treatment at Week 52. Participants will be dosed approximately once Q4W throughout the duration of the open-label extension period. The duration of the open-label extension period will vary depending on the date of enrollment of the participant in the study. The study is expected to continue until BIIB092 is commercially available, the development program is terminated, or the study is terminated at the discretion of the Sponsor, whichever comes first.

CONFIDENTIAL

The information contained herein may not be used, disclosed, or published without the written consent of Biogen MA Inc.

5.1.2. Study Visits

Study visits will be conducted approximately Q4W. Study treatment will be administered and safety, efficacy, and other assessments will be performed (Table 1, Table 2, Table 3, and Table 4). The study will generally be conducted on an outpatient basis unless some procedures would be better performed on an inpatient basis based on the needs of the participant.

Participants will be observed and monitored by study personnel for approximately 2 hours after the end of an infusion. Participants with ongoing AEs or SAEs will remain at the site or be sent to an inpatient monitoring facility until the Investigator has determined that these events have resolved or do not require inpatient monitoring.

5.1.3. Study Assessments

- Participants will be closely monitored for safety throughout the study. Physical examinations, vital sign measurements, 12-lead electrocardiograms (ECG), and clinical laboratory evaluations, including assessments for immunogenicity will be performed. AEs will be closely monitored. Suicidality will also be assessed by completing the [REDACTED]
- PSP-related signs, symptoms, and quality of life will be assessed using the following clinical assessments: PSPRS, MDS-UPDRS Part II, SEADL scale, CGI-S, CGI-C, MoCA, European Quality of Life (EuroQol) version [REDACTED] and PSP-QoL and neuropsychological testing (RBANS, phonemic fluency, LNS, and CTT).
- Caregiver burden will also be assessed [REDACTED]
- Blood will be collected for immunogenicity, PK, PD, and exploratory biomarker analysis from each participant during this study in the double-blind period and in the open-label extension period.
- Structural changes in the brain will be assessed using MRI. It is anticipated that each participant will have total of 4 MRIs over the course of the study, including an MRI during the screening period (up to Day -14) and at Weeks 24, 52, and 100.
- [REDACTED]
- [REDACTED]
- [REDACTED]
- [REDACTED]
- [REDACTED]
- [REDACTED]
- [REDACTED]
- Participants in the QMA substudy will undergo quantitative assessments of core motor features of PSP using wearable sensors to measure gait, postural instability, motor function, and falls

5.1.4. Home Visits

After Week 24, except for those visits when clinical scales, LPs, or MRI assessments are performed, visits and procedures may be performed in the home as long as appropriate services

CONFIDENTIAL

The information contained herein may not be used, disclosed, or published without the written consent of Biogen MA Inc.

are available to perform the required study procedures and adequately monitor for potential safety events. In the double-blind period of the study, Weeks 28, 32, 40, and 44 may qualify for home visits.

In the open-label extension period of the study, Week 68, 72, 80, 84, 92, 96, 104, 108, 116, 120, 128, 132, 140, 144, 152, 156, 164, 168, 176, 180, 188, and 192 visits may qualify for a home visit. However, in the event that the participant experienced a clinically significant infusion reaction during the first 24 weeks of the protocol, the participant should not be administered BIIB092 in the home unless previously approved by the Study Investigator.

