Phase 2b Study of BIIB092 in Participants with Progressive Supranuclear Palsy

██████████; LP = lumbar puncture; MDS-UPDRS = Movement Disorder Society-sponsored revision of the Unified Parkinson's Disease Rating Scale; MoCA = Montreal Cognitive Assessment; NSAE = non-serious adverse event; PK = pharmacokinetic; MRI = magnetic resonance imaging; NE = neurological examination; PSP = Progressive Supranuclear Palsy; PSPRS = Progressive Supranuclear Palsy Rating Scale; QoL = quality of life; RBANS = Repeatable Battery for the Assessment of Neuropsychological Disease Severity; ██████████; SAE = serious adverse events; SEADL = Schwab and England Activities of Daily Living scale; ██████████ WOCBP = women of childbearing potential.

- ^a Efficacy assessments requiring participant involvement should be completed prior to dosing with study treatment unless otherwise specified in the notes; specific attention should be paid to conducting the Week 24 MRI within 7 days prior to the Week 24 dosing visit. The study visits at Weeks 0, 12, 24, 36, 48, 52, and Early Discontinuation, which involve the conduct of efficacy assessments, may be completed over a period of up to 3 consecutive days.
- ^b Weeks 28, 32, 40, and 44 may qualify for a home visit if appropriate. See Section 5.1.4 for details.
- ^c Participants who discontinue study treatment during the double-blind period of the study (prior to Week 52) and remain enrolled in the study will be expected to complete scheduled safety and efficacy evaluations at Weeks 12, 24, 36, 48, and 52 until the decision is made to withdraw from the study.
- ^d Early Discontinuation visit procedures should be completed for any participant who discontinues study treatment and also withdraws from the study at any time prior to Week 52. Participants who withdraw from the study should be encouraged to return to the clinic at Week 52 to complete the Week 52 procedures. If the visit cannot be done in person by the participant, the site should attempt a phone call at approximately Week 52 to collect at a minimum vital status (whether the participant is alive or dead) and SAE/AE information on the participant.
- ^e This 30-day assessment of AEs/SAEs may be done by phone if no visit occurs.

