AE = adverse event; CGI = Clinical Global Impression; CSF = cerebrospinal fluid; ██████████ CTT = Color Trails Test; ECG = electrocardiogram; ██████████ LNS = Letter-Number Sequencing; LP = lumbar puncture; MDS-UPDRS = Movement Disorder Society-sponsored revision of the Unified Parkinson's Disease Rating Scale; MoCA = Montreal Cognitive Assessment; MRI = magnetic resonance imaging; NE = neurological examination; NSAEs = Non-Serious Adverse Events; PK = pharmacokinetic; QoL = quality of life; PSP = Progressive Supranuclear Palsy; PSPRS = Progressive Supranuclear Palsy Rating Scale; RBANS = Repeatable Battery for the Assessment of Neuropsychological Disease Severity; ██████████ SAEs = serious adverse events; SEADL = Schwab and England Activities of Daily Living scale; ██████████; WOCBP = women of childbearing potential.

^a Weeks 68, 72, 80, 84, 92, 96, 104, 108, 116, 120, 128, 132, 140, 144, 152, 156, 164, 168, 176, 180, 188, and 192 may qualify for home visits if appropriate. See Section 5.1.4 for details.

^b Participants who discontinue study treatment during the open-label extension period of the study (after Week 52) but remain enrolled in the study will be expected to complete scheduled safety and efficacy evaluations at Weeks 64, 76, 88, 100, 112, 124, 136, 148, 160, 172, 184, and 196.

^c Sample to be collected predose.

^d This 30-day assessment of AEs/SAEs may be done by phone if no visit occurs.

CONFIDENTIAL

The information contained herein may not be used, disclosed, or published without the written consent of Biogen MA Inc.

Table 4: Quantitative Assessment Procedural Outline for the Extension Period Substudy

Quantitative Movement Assessments	Substudy Enrollment in the Open-Label Extension Period		
	Baseline Visit ^a	Three-Month Follow-Up Visit ^b	Six-Month Follow-Up Visit ^b
In-Clinic Assessments			
Orthostatic vitals	X		
Visual acuity	X		
Joint-position test	X		
Strength test for hip flexion and knee extension	X		
Sway	X	X	X
Gait	X	X	X
Timed chair stands	X	X	X
Instrumented push and release test	X	X	X
Toe taps	X	X	X
Wrist rotations	X	X	X
In-Home Assessments			
Falls ^c		X	

QMA = quantitative movement assessments

^a The QMA substudy baseline visit will start after participants sign the informed consent form and are eligible to enroll in the substudy.

^b Two follow-up visits will be conducted at 3 and 6 months after the baseline visit of the QMA substudy.

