5.6. Scientific Rationale for Study Design

The double-blind period of the study is intended to determine the efficacy and safety/tolerability of BIIB092. It is anticipated that participants will be randomized in a 2:1 ratio to receive 2000 mg of BIIB092 or placebo, respectively, administered by IV infusion once Q4W for approximately 48 weeks (up to a total of 13 times). The justification for the dose is described in Section 5.7 and based on previous studies evaluating the PK of BIIB092 and PD effects on unbound N-terminal tau levels in CSF. A duration of treatment of up to 52 weeks and comparison with a placebo control are considered adequate and appropriate to evaluate the efficacy of BIIB092 on the primary and secondary endpoints, given the natural history of PSP and the lack of any approved therapies.

The open-label extension period of the study is intended to further characterize the long-term efficacy and safety/tolerability of BIIB092. It is anticipated that all participants in the study, including those randomized to receive placebo in the double-blind period, will receive 2000 mg of BIIB092 administered Q4W by IV infusion throughout the open-label extension period of the study.

CONFIDENTIAL

The information contained herein may not be used, disclosed, or published without the written consent of Biogen MA Inc.

The QMA substudy in the open-label extension period is intended to further characterize disease progression with wearable sensors. Postural instability, gait disturbances, and falls are prominent signs of PSP that impact participant outcomes. At present these signs are assessed in the clinic with questionnaires. It is anticipated that advances in wearable sensor technology and analytics could improve quantification of these signs and may provide sensitive measures of disease progression.

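### The approval rule for home BIIB092 counts only infusion reactions in the first 24 weeks of the protocol, when participants who later cross over from placebo have had no BIIB092

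*Protocol*

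**What the plan says.** Protocol Section 5.1.4 allows some infusion visits at home after Week 24, provided that services "are available to perform the required study procedures and adequately monitor for potential safety events". In the double-blind period, "Weeks 28, 32, 40, and 44 may qualify for home visits". In the extension, the home-eligible visits start at Week 68 and run to Week 192. Straight after that list comes the restriction: BIIB092 is not to be given at home, unless the Investigator has approved it beforehand, "in the event that the participant experienced a clinically significant infusion reaction during the first 24 weeks of the protocol". The overview sections (1.1) of both SAPs repeat the 24-week window.

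The footnotes to the schedules refer back to this section. Table 2 footnote b reads "Weeks 28, 32, 40, and 44 may qualify for a home visit if appropriate. See Section 5.1.4 for details". Table 3 footnote a lists the extension weeks that "may qualify for home visits if appropriate. See Section 5.1.4 for details".

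On dosing, Section 5.1.1 has participants "dosed approximately once every 4 weeks (Q4W) up to a total of 13 times" in the double-blind period, with the last of those doses at Week 48. Those who continue "will receive the first dose of the open-label study treatment at Week 52". Section 5.6 anticipates that all participants, "including those randomized to receive placebo in the double-blind period, will receive 2000 mg of BIIB092" every 4 weeks through the extension. Section 7.1 gives the placebo as saline or dextrose.

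**The concern.** The rule should catch a participant who has already reacted to an infusion before the next one moves out of the clinic. It is tied to calendar time in the protocol, not to exposure. For a participant who crosses over from placebo, the window closes 28 weeks before the first BIIB092 dose (52 − 24 = 28).

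Followed as written, a clinically significant reaction to saline or dextrose at Week 8 requires approval before home BIIB092. The same reaction to BIIB092 itself at Week 56 does not, although home dosing opens 12 weeks later. The wording also passes over any active-arm reaction after Week 24.

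At stake is a documented approval step before BIIB092 is given at home after an earlier reaction to it. The concern is not unattended dosing or loss of all oversight, and it does not bear on any efficacy endpoint.

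**Working it through.** **Inputs**

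- Look-back window: first 24 weeks of the protocol (Section 5.1.4).
- Double-blind infusions: every 4 weeks, Week 0 to Week 48 (Section 5.1.1).
- First open-label infusion: Week 52, then every 4 weeks (Section 5.1.1).
- Home-eligible visits: Weeks 28, 32, 40 and 44; in the extension, from Week 68 (Section 5.1.4).
- Prior BIIB092 exposure is prohibited (Section 7.7.1), so placebo participants have none before Week 52.
- 153 participants randomized to placebo, about 25% dropout, about 115 expected to complete Week 52 (Section 5.4).

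**Step 1. Reproduce the dosing schedule.** Weeks 0, 4, …, 48 give 48/4 + 1 = 13 infusions, matching the stated maximum of 13.

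**Step 2. Count infusions in the window.** Weeks 0, 4, 8, 12, 16, 20 and 24 make 7 infusions, counting the Week 24 visit as inside.

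| | Active arm | Placebo to BIIB092 |
|---|---|---|
| BIIB092 infusions in the window | 7 | 0 |
| Placebo infusions in the window | 0 | 7 |
| First home-eligible BIIB092 visit | Week 28 | Week 68 |
| BIIB092 infusions before that visit | 7 (Weeks 0–24) | 4 (Weeks 52, 56, 60, 64) |
| Of these, in the window | 7 of 7 | 0 of 4 |

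For the active arm the window works as an entry gate, because every infusion before the first home-eligible visit counts. For crossover participants none does.

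**Step 3. Active arm after the window.** Double-blind infusions at Weeks 28, 32, 36, 40, 44 and 48 make 6, of which 4 are home-eligible and 2 (Weeks 36 and 48) are in clinic. Reactions at any of these do not trigger the rule for later home visits.

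**Step 4. Could the phrase mean 24 weeks from first BIIB092?** The text does not say so, and nothing in the protocol or SAPs resets the window at Week 52. Such a window would run from Week 52 to Week 52 + 24 = Week 76. Weeks 68 and 72, which are already home-eligible, would fall inside it, so it would not work as the entry gate it is for the active arm.

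**Step 5. Number of people.** 153 × 0.75 = 114.75, the expected 115 or so placebo completers. This is an upper bound on crossover participants, reached only if all enter the extension. The documents give no rate of clinically significant infusion reactions. Assuming 1% to 5% have one at Weeks 52–64:

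- 115 × 0.01 = 1.15
- 115 × 0.05 = 5.75

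That is about 1 to 6 people whose reaction to BIIB092 would not trigger the rule, and fewer if some do not enter the extension or are never dosed at home.

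**The case against.** The strongest reply is that much else stands between a reaction and an unsafe home infusion.

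- Home visits are permitted, not required. The schedule footnotes make them subject to appropriateness, and Section 5.1.4 requires adequate monitoring services.
- Crossover participants get four in-clinic BIIB092 infusions before any home dose. Weeks 56 and 60 are kept in clinic although no clinical scales, lumbar puncture or MRI are due then.
- Infusions are monitored (Section 7.4). Participants are observed for about 2 hours afterwards, and those with ongoing adverse events are held until the Investigator clears them (Section 5.1.2). Epinephrine is dispensed for home visits (Section 7).
- The Investigator must stop treatment for an adverse event that makes continuing against the participant's interest (Section 8.1). Immediate safety concerns go to the Medical Monitor (Section 9), and the DMC reviews unblinded data (Section 5.3).
- The open-label extension SAP tabulates infusion reactions by clinic versus home (Section 6.2.5).

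These points are correct, and they lower the risk. They govern whether a visit may suitably be at home, how a reaction is handled, whether treatment continues, or how events are reported. None is a written rule on where the next infusion is given after a reaction. Section 7.4 refers acute reactions to Section 14, which is silent on location. The in-clinic run-in would be the natural basis for the approval decision, but the rule does not use what is seen there.

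It can also be said that a rule used under blinding has to count placebo reactions, and that the amended wording would still count them. That stands: counting them is conservative and does no harm. The defect is that later reactions to BIIB092 are left out.

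Two smaller points also stand. The Week 24 target visit is Day 169 in the placebo-controlled SAP (Section 5.1.1, Table 2), while 24 weeks end on Day 168. On a strict reading the active-arm count is therefore 6 of 7; the crossover count of 0 of 4 does not change. And Section 7.5 gives the DHA precedence over the protocol, so an instruction there on home dosing after a reaction cannot be excluded.

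**Conclusion.** The concern holds. Read literally, the approval rule excludes all 4 BIIB092 infusions that a crossover participant receives before home dosing opens, and all active-arm infusions from Week 28 onward. Confidence is high for the text of Section 5.1.4; whether sites have a separate instruction depends on the DHA.

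The practical size is modest: at most about 115 crossover participants, and about 1 to 6 missed triggers under the assumed 1% to 5% reaction rate. These are people for whom the approval step would not be required, not people expected to be harmed. The change should still be made, because a stated safety rule misses the reactions it exists to catch and the correction is cheap.

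**What to change.** In Protocol Section 5.1.4, replace the 24-week look-back with: *at any earlier study infusion, including open-label infusions from Week 52*. Apply it to all participants whatever their original assignment, and keep the Investigator's power to approve home dosing. Because the wording does not depend on assignment, it needs no unblinding. It covers both crossover reactions at Weeks 52–64 and later active-arm reactions.

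Check the DHA for any conflicting instruction. The matching sentences in Section 1.1 of both SAPs can be aligned for consistency, with no effect on any analysis. Table 2 footnote b and Table 3 footnote a can stay as they are, since they refer to Section 5.1.4.

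The cost is one protocol clause and two optional SAP edits. In operation, a few home visits may need an approval note or move to the clinic. The visit schedule and the analyses do not change.
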